#### 1. Health Impact and users perception

- Do users take up SRH and maternal health products and services because of our innovation or regardless of it? (In other words, are we stimulating new SRH users or are the members previously active SHR clients?)
- When they first enrolled in the program, were they using contraceptives or are their first-time users? Did the platform make it easier for them? How? What other benefit appeal? If they were switchers, what were the motivators to switch from their previous source of health services to ours?
- How often did they use the platform? If they were repeat users, what was their motivation to come back to the platform? If they were only one time users, why did they not come back?
- Does the Tiko digital platform increase consistent use of short-term contraceptive methods? Why or why not?
- Does the Tiko digital platform increase consistent MNCH behaviours? Why or why not?
- What did they like about the platform and the experience? What barriers did it solve for them? Will they use it again? Will they recommend their friends to use?
- Why did they choose Tiko platform? What would they have done if it were not available as an option?
- What perception or behaviour shifts have our intervention been able to address around stigma, access, privacy, dignity/respect, willingness to pay, etc?

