## 2 Research Methods

### 2.1 Overview of methods

This evaluation will be a mixed methods observational design with mainly descriptive and exploratory analysis. The desk research will review documents, secondary data public available (such as NFHS), and any App background data (deidentified) to better understand the programme.

This is followed by qualitative surveys for which 40 in-depth interviews of various beneficiaries and programme stakeholders (demand creators, service providers, lifestyle partners) will be conducted in person or over phone.

Depending on the insights, we will develop a structured quantitative questionnaire and administer the in-person survey to approx. 480 beneficiaries of SRH and MCH services (total). These surveys will seek information on knowledge, practices, barriers, enablers for SRH and MCH services, exposure o Tiko platform, and how it helped or did not help. The survey participants will be women (18-35years of age) who had subscribed to Tiko card between 2018 and 2020. A subset of these would be regular users, a subset will be sporadic

or one-time user and remaining will be 'non-users'. The sample will try to get adequate representation from all categories.

The in-person surveys will be followed with shorter (10-15 minutes) phone surveys with 1200 active users and 600 non-users who had enrolled on Tiko platform. Phone surveys will collect only basic information needed to confirm findings from in-person and qualitative surveys.

The analysis will triangulate the insights from both qualitative and quantitative analysis. We mainly anticipate descriptive analysis to tabulate indicators related to knowledge, practices, barriers, enablers w.r.t. SRH and MCH services, exposure and use of Tiko platform, how it has helped or not helped or affected their well being, suggestions and preferences for different components of the platform, etc. We anticipate cross tabulation by socio-economic characteristics, regions (say by Cities), and duration of use.

While no analytical tests are anticipated at this time, we expect to conduct standard bivariate tests (t-test and chi2 test) and regression analysis for more nuanced group mean tests or multiple comparison tests (logit, OLS, mixed models). We will be adjusting for standard errors for robust inference. In case of statistical inference, we expect one side test with alpha < 0.1 to consider a relationship or test statistic significant.

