#### 2.2 Sample Design and Power Calculations

For detailed 45-50 minutes in-person surveys, 570 respondents will be interviewed across Rajasthan, Uttar Pradesh and Delhi, of which we expect to complete 480 interviews. This sample size was determined on basis of measuring a proportion of 50% with 5 pp error rate and 95% confidence which yields n of 384 and this n was increased by design effect of 1.25 to account for clustering if any at the city level. In person surveys will be done in Agra, Jaipur

For phone surveys, we designed a sample of 2000 complete surveys. Moreover, over sampling will be done in Rajasthan, Uttar Pradesh and Delhi to ensure at least 50 interviews in each city. This sample is designed such that we can conduct descriptive analysis for 3-4 sub-groups (say by cities or by socio-economic categories) with at least 300-400 sample in

each sub-group. The purpose of phone surveys will be to add more statistical power to limited in-person sample size we have for few key questions of interest.

We also expect that the phone surveys and in-person data will be used for statistical group mean tests between regular users and one-time or non-users to compare SRH and ANC related practices between the two groups. It is not a controlled trial of Tiko platform but will be exploratory to understand additionality in service usage of regular users if any.

Assuming at least 150 regular and 150 non-users included in the in-person surveys, the sample will have power to detect 25% relative change or 0.25 SD change from an outcome distributed binomially with mean of 0.50 or with standardized normal distribution with mean 0 and SD of 1 N $^{\circ}(0,1)$  with power of 80% and Type I error of 0.10 with one sided test.

Assuming 500 regular and 500 non-users included in the in-person surveys, the sample will have power to detect 15% relative change or 0.15 SD change from an outcome distributed binomially with mean of 0.50 or with standardized normal distribution with mean 0 and SD of 1 N~(0,1) with power of 80% and Type I error of 0.10 with one sided test.

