#### 2.6 Quantitative Data Quality Assurance, Processing and Analysis

We would conduct 20% centralised back-checks over phone to ensure in-person visits actually happened and cross-check factual data. For phone surveys, 20% audio- listening-in checks by the coordinator/monitor will be done to cross-verify the factual data. Apart from this, thorough back-office data quality checks (outliers, straight line responses, etc) will be done on pre-identified important variables. A researcher will ensure accuracy of data every third day of the survey by using high-frequency data quality checks for quantitative surveys.

Quantitative data will be entered in a CAPI App on ODK system, transmitted to secure server with 16-key encryption, and downloaded to a dedicated desktop for data. The data will be deidentified immediately first. Second, the processing will include giving variable and value labels, removing duplicate submissions if any, coding open ended responses if they exceed 5% of any categorical question's answers, etc. Then, this de-identified and processed data is submitted to researchers for further analysis in STATA format.

We mainly anticipate descriptive analysis to tabulate indicators related to knowledge, practices, barriers, enablers w.r.t. SRH and MCH services, exposure and use of Tiko platform, how it has helped or not helped or affected their well-being, suggestions and preferences for different components of the platform, etc. We anticipate cross tabulation by socio-economic characteristics, regions (say by Cities), and duration of use.

While no analytical tests are anticipated at this time, we expect to conduct standard bivariate tests (t-test and chi2 test) and regression analysis for more nuanced group mean tests or multiple comparison tests (logit, OLS, mixed models). We will be adjusting for

standard errors for robust inference. In case of statistical inference, we expect one side test with alpha < 0.1 to consider a relationship or test statistic significant.

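### The additionality comparison of regular users with one-time or non-users is not tied to any adjustment for city or for contraceptive use at enrolment, so an unadjusted difference could reflect either

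*Protocol*

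**What the plan says.** Section 2.2 states that the phone and in-person data "will be used for statistical group mean tests between regular users and one-time or non-users", comparing SRH and ANC practices. It qualifies this: "It is not a controlled trial of Tiko platform but will be exploratory to understand additionality in service usage of regular users if any". The power statements there are for simple two-group contrasts at one-sided alpha 0.10.

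Section 2.3 defines non-users as enrolled women minus users, so each woman's own behaviour decides her group.

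Section 1.3 names the rival explanation: "are we stimulating new SRH users or are the members previously active SHR clients". It also asks: "When they first enrolled in the program, were they using contraceptives or are their first-time users".

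For methods, section 2.6 lists "standard bivariate tests (t-test and chi2 test") and sections 2.1 and 2.6 add "regression analysis for more nuanced group mean tests or multiple comparison tests (logit, OLS, mixed models"). No covariates are named. The only adjustment described is of standard errors, for "robust inference". The cross-tabulation factors are socio-economic characteristics, region and duration of use; prior use is not among them.

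**The concern.** The first research question is whether women take up services because of the platform or would have done so anyway. A difference in current practice between groups defined by platform use cannot separate the two. Women who become regular users may have differed in contraceptive practice before enrolment, and they live in different cities in different proportions. Robust standard errors change the stated uncertainty of a difference; they do not remove confounding from it. The phone survey is meant to add statistical power, and a larger sample only makes a biased difference more likely to pass the one-sided 0.10 threshold.

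Timing matters too. A covariate can be chosen after fieldwork, but a baseline question that was never put to non-users cannot be recovered. Section 2.5 describes the questionnaires as drafts, so the question can still be added.

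**Working it through.** **1. The plan's own power figures (section 2.2).** One-sided alpha 0.10, so z = 1.2816. Power = Φ(d·√(n/2) − 1.2816).
- 150 per group, d = 0.25: 0.25 × √75 = 2.165, giving power 81.2%. For 0.50 v 0.625 the power is 81.8%. The stated 80% is reproduced.
- 500 per group, d = 0.15: 0.15 × √250 = 2.372, giving power 86.2%. For 0.50 v 0.575 it is 86.4%. The stated 80% is conservative.

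The binary targets are 0.25 × 0.50 = 12.5 points and 0.15 × 0.50 = 7.5 points. These powers apply to unadjusted contrasts and say nothing about confounding.

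**2. City imbalance, from the allocation tables in section 2.3.**

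| Survey | City | Non-users | Users |
|---|---|---|---|
| Phone | Agra | 347/500 = 69% | 527/1500 = 35% |
| Phone | Jaipur | 28/500 = 6% | 691/1500 = 46% |
| In-person | Agra | 100/150 = 67% | 150/350 = 43% |
| In-person | Jaipur | 50/150 = 33% | 200/350 = 57% |

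The tables split users from non-users. They do not separate regular from one-time users, so the imbalance for the exact contrast in 2.2 may differ somewhat.

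False difference from city = (gap in practice between Agra and elsewhere) × (imbalance in Agra share). The gap is not in the documents. For an assumed 10-point gap:
- Phone: 10 × (0.694 − 0.351) = 3.4 points.
- In-person: 10 × (0.667 − 0.429) = 2.4 points.

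City alone would need a gap of about 7.5/0.343 = 22 points to imitate the 7.5-point target in the phone survey, and about 12.5/0.238 = 53 points to imitate the 12.5-point target in person. The imbalance is certain; its effect depends on how far practices differ by city.

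**3. Prior use, illustration only.** Suppose no platform effect, and let current use be a among prior users and b among others. Each group's rate is q·a + (1 − q)·b, where q is its share of prior users. The false difference is (a − b) × (gap in q). With a = 80% and b = 30%, both assumed:
- q = 40% in non-users and 50% in regular users: 0.5 × 10 = 5 points, significant in 34% of studies at 150 per group and 62% at 500.
- q = 40% and 60%: 0.5 × 20 = 10 points, significant in 68% and 97%.

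The nominal rate is 10%. Over a wider set of assumptions (prior users 70–90%, others 20–40%, imbalance 10–30 points) the false difference runs from 3 to 21 points and is significant in 22–99% of studies at 150 per group and 37–100% at 500. Comparing within levels of prior use removes it in this model.

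**4. Will the baseline exist in both groups?** The question in 1.3 sits under a heading about users. Section 2.5 lists the in-person tool for enrolled users, although 2.3 plans 150 in-person non-users. Section 2.1 limits the phone survey to basic information. The questionnaires themselves are annexures not shown. The protocol neither confirms nor rules out that non-users are asked.

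**The case against.** A reader might infer that the plan commits to an unadjusted test, ignores a baseline it already holds for both groups, and will present the result as a platform effect. The documents do not support this.
- Regression for group mean tests is planned in 2.1 and 2.6, and prior use is nowhere excluded from it. A covariate list is commonly left to the SAP, which is not shown.
- A research question about use at enrolment does not show that non-users are asked it.
- Section 2.2 disclaims a controlled trial and calls the comparison exploratory. Section 2.1 describes mainly descriptive work with triangulation, and 1.3 also asks what women would have done without the platform.
- The direction of bias is not documented. Women with an established source of care might enrol, keep that source and become non-users, which would reverse it.
- Contraceptive status at enrolment is not a baseline for ANC outcomes.

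All of this stands, and it limits the point. It does not dispose of it. The city imbalance is built into the protocol's own allocation, the protocol itself raises prior use as the competing explanation, and the baseline question has to be in the tools before fieldwork. Calling the comparison exploratory does not make an unadjusted difference informative about additionality.

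**Conclusion.** The point holds as a worthwhile improvement to the method. It does not show that the plan fixes an unadjusted analysis. The protocol sets up a comparison meant to inform additionality between self-formed groups with strongly unequal city mixes, and does not connect it to the regression it lists or to the enrolment-time status it asks about. An unadjusted difference could reflect prior behaviour or city.

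The city shares are facts of the section 2.3 tables. The bias they cause depends on city differences in practice that the documents do not give. The size and direction of any prior-use bias are likewise unknown; the 5- and 10-point figures rest wholly on assumed rates.

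**What to change.** In sections 2.2 and 2.6:
- Make the already listed logit or OLS regression of current practice on user group the main additionality comparison, adjusted for city, age, enrolment year and, where the surveys are pooled, survey mode.
- For contraceptive outcomes, also adjust for use at enrolment and show results separately for prior and first-time users.
- For ANC outcomes, use a relevant baseline instead, such as parity or prior ANC.
- Keep the t-test and chi2 results as secondary, and report everything as association.

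In the draft tools, ask the enrolment-use question in the same words of users and non-users, in both surveys.

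The cost is analysis wording and one added question wherever it is absent; the ANC baseline also has to be available for both groups. Enrolment-time use is recalled, so some residual confounding will remain.

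### The in-person power statement assumes at least 150 regular users, but the sampling steps fix only users and non-users, so the number of regular users is left to chance

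*Protocol*

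**What the plan says.** Protocol section 2.1 recognises three kinds of enrolled women: regular users, sporadic or one-time users, and non-users ("A subset of these would be regular users, a subset will be sporadic"). On their numbers it says only: "The sample will try to get adequate representation from all categories".

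Section 2.2 plans "statistical group mean tests between regular users and one-time or non-users" and gives the in-person power as follows: "Assuming at least 150 regular and 150 non-users included in the in-person surveys, the sample will have power to detect 25% relative change". In standardised units that sentence puts the effect at 0.25 SD, and it sets 80% power and a one-sided type I error of 0.10. A parallel sentence gives 0.15 SD and begins "Assuming 500 regular and 500 non-users included in the in-person surveys".

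Section 2.3 sets the sampling. In-person step 2 fixes two strata, 150 non-users and 350 users. The later steps allocate by city and Pro Agent, take a random list of beneficiaries for each sampled agent, and call down that list. The phone steps do the same with 500 non-users and 1500 users. The frame table counts only actual users and non-users. No step uses frequency of use, and the protocol does not define a regular user.

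**The concern.** One of the two group sizes behind the in-person power is a fixed stratum and the other is not. The 150 non-users are secured by design. The 150 regular users are whatever a random draw of 350 users yields, and the documents give no figure from which to predict it.

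Section 2.2 uses this comparison to explore whether regular use goes with additional SRH and ANC practices. If regular users are scarce, the comparison will detect only larger differences than the protocol states. A later analysis plan cannot repair this, because regular users who were not put on the lists cannot be added at analysis.

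**Working it through.** **Inputs.** From section 2.2: 150 regular users and 150 non-users, 0.25 SD or 0.50 against 0.625 (25% relative), one-sided 0.10, power 80%, 480 expected completed interviews. From section 2.3: 350 users and 150 non-users in person; 1500 and 500 by phone. From section 2.1: 1200 and 600 by phone. The share of users who are regular is in neither the text nor the tables, so it is assumed over a range. Observations are taken as independent.

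**Formulas (means).** Power = Φ(0.25/√(1/n₁ + 1/n₀) − 1.2816). Effect detectable with 80% power = (1.2816 + 0.8416) × √(1/n₁ + 1/n₀) = 2.1232 × √(1/n₁ + 1/n₀). For proportions, the usual two-sample test with pooled variance under the null.

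**Step 1: the protocol's own figure.** For 150 against 150, √(2/150) = 0.1155, so power = Φ(2.165 − 1.282) = 81.2%, and the detectable effect is 0.245 SD. For proportions, power is 81.8%. The stated 80% reproduces.

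**Step 2: share needed for the assumed 150.** 150/350 = 42.9%.

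**Step 3: power over assumed shares, 150 non-users.**

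| Regular share of 350 (assumed) | Regular users | Power, means | Power, proportions | Detectable effect (SD) |
|---|---|---|---|---|
| 20% | 70 | 67.2% | 67.7% | 0.31 |
| 30% | 105 | 75.3% | 75.9% | 0.27 |
| 40% | 140 | 80.1% | 80.8% | 0.25 |
| 50% | 175 | 83.3% | 83.9% | 0.24 |
| 60% | 210 | 85.5% | 86.1% | 0.23 |

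Under simple binomial sampling of 350 users, the chance of reaching 150 regular users is essentially nil at a 30% share, 15% at 40% and over 99% at 50%.

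**Step 4: break-even for 80%.** For means, 1/n₁ = (0.25/2.1232)² − 1/150 = 0.01386 − 0.00667 = 0.00720, so n₁ = 139, or 39.7% of 350. For proportions n₁ = 134, or 38.3%. If the 480 expected completes split 70:30 (assumption: 336 users, 144 non-users), the means figure becomes 145, and 145/336 = 43%.

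**Step 5: the phone survey.** Five hundred against 500 gives 86.2% for 0.15 SD. Reaching 500 regular users takes 500/1500 = 33% on the section 2.3 strata, or 500/1200 = 42% on the section 2.1 numbers. For 80% power, (0.15/2.1232)² = 0.00499. Subtracting 1/500 gives 335 regular users (22% of 1500); subtracting 1/600 gives 301 (25% of 1200).

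**Step 6: users against non-users.** For 350 against 150, √(1/350 + 1/150) = 0.0976, so power = Φ(2.562 − 1.282) = 90.0% for 0.25 SD.

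**The case against.** The strongest reply is that the 150 is worded as an assumption, not promised as a target. The in-person sample size comes from precision (384 × 1.25 = 480), not from this comparison, and section 2.2 calls the comparison exploratory. There is room for 150 regular users among 350. Section 2.2 also expects both surveys to feed these tests. Pooling them (350 + 1500 = 1850 users, 150 + 500 = 650 non-users, independence assumed), even a 10% regular share would give 96% power for 0.25 SD. All of this stands, and it limits the weight of the point. It does not cover questions asked only in person, since "Phone surveys will collect only basic information needed to confirm findings from in-person and qualitative surveys". Nor does the intention to represent all categories supply a number or a method.

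Three stronger readings are tempting, and the documents do not support them.

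- A reader might infer that the comparison is underpowered. Without a regular share this cannot be said: above about 40% of the 350, power exceeds 80%.
- A reader might infer that the mismatch between the comparator described in section 2.2 and the non-users used for its power invalidates the figure. At a fixed 0.25 SD, adding sporadic and one-time users to the comparator raises power (150 against 350: 90%; 105 against 395: 84%). The mismatch is a matter of wording.
- A reader might infer that the design effect belongs in the power, because "this n was increased by design effect of 1.25 to account for clustering if any at the city level" while the sampled clusters are Pro Agents. The full 1.25 would give 74%, but it would apply to the difference only if each agent supplied a single type of woman, which nothing in the protocol suggests. In an illustration with 100 agents, 5 interviews each and an intra-agent correlation of 0.0625 (all assumed), the factor on the difference is 0.96 to 1.00 when types mix within agents. The protocol also says: "We will be adjusting for standard errors for robust inference". Clustering is therefore no part of this point.

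**Conclusion.** The point holds as a minor to moderate one that is cheap to act on. The power calculation is correct for the group sizes it assumes, but the sampling plan secures only one of them. The stated 80% holds if about 38-40% or more of the 350 users are regular, or about 43% (means) if the 480 completes split 70:30. The protocol gives no share. Below those values the loss is moderate: 75% power at an assumed 30%, 67% at an assumed 20%. These figures rest on independent observations and a comparator of non-users only. The consequence falls mainly on items asked only in person.

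**What to change.** 1. Define a regular user by a transaction-count cut-off. Section 2.1 says that the app data hold each transaction.
2. When the beneficiary lists are drawn (section 2.3, in-person step 6), split the user stratum into regular and sporadic or one-time users, with a minimum of 150 regular.
3. Apply the same split to the phone user stratum, after reconciling 1500 users and 500 non-users in section 2.3 with 1200 and 600 in section 2.1.
4. If no split is made, state the regular share that the 80% requires, or restate power for users against non-users (90% for 0.25 SD at 350 against 150).
5. Wording: the 500 against 500 sentence should not say in-person, because 1000 women exceed that survey and only the phone strata can hold them. Name one comparator.

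**Cost.** The database holder sorts the lists by transaction count. Contact lists may need to be longer if regular users are scarce, given the 30-40% response expected in section 2.3. If the minimum binds (a share s below 43%), overall user estimates need weights. With a 150/200 split the variance factor is s²/(3/7) + (1 − s)²/(4/7). At assumed shares of 40%, 30% and 20% it is 1.003, 1.068 and 1.213, so the effective user sample falls from 350 to 349, 328 or 288. At 30%, the margin of error around a 50% proportion widens from 5.2 to 5.4 points.

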#### 2.3 Sampling for In-Person and Phone-Surveys

The sample frame for both surveys will be the Tiko beneficiary database available with Triggerise. Below is the summary of viable database sample frame (exclude smaller sites where the programme is too small to be considered in this study)

Stata	City	Area	Number of		
Sidle			Enrollments	Actual Users	Non-Users
Uttar Pradesh	Agra	Both	34,726	21,743	12,983
Rajasthan	Jaipur	Both	29,588	28,531	1,057
Rajasthan	Ajmer	Urban	7,325	4,532	2,793
Rajasthan	Tonk	Peri Urban	5,176	3,993	1,183
Delhi	Delhi	Urban	3,846	3,142	704
Uttar Pradesh	Firozabad	Peri Urban	1,044	119	925
TOTAL			81,705	62,060	19,645

The following steps will be followed for sampling of in-person survey respondents:

- 1. Restrict the study to only Jaipur and Agra which constitutes 70% of the enrollments and 84% of the actual user base.
- 2. Stratify sample as 150 non-users (enrollment minus users) and 350 users
- 3. Distribute sample in approx. proportion to the actual numbers in both cities for users and non-users as below.

City	Non-users	Actual Users	Total
Agra	100	150	250
Jaipur	50	200	250
Total	150	350	500

- 4. Distribute the sample across the 'Tiko Pro Agents' working in the city. We currently don't have this data, but we expect to complete at least 5 interviews per agent and spread the sample to cover about 25% of the agents working in the city.
- 5. Based on above, randomly sample the Pro Agents from database that will be made available by Triggerise.
- 6. Obtain a list of randomly sampled Beneficiaries from Triggerise for each sampled pro agent. We will obtain 3-times the number of completed interviews required per agent because our scoping visit suggests expecting 30-40% response rate in finding the beneficiary house with help of agent and then getting their consent for the interview. If required, Triggerise will make available more beneficiaries (their name and phone numbers per agent) if the sample size is not achieved.
- 7. NEERMAN enumerators will call each beneficiary sequentially in the list and fix appointments for the in-person interview. The phone records will track validity of numbers, refusals, and consents. Pro agent's help will be sought to find address or in field logistics or to establish our enumerators' bona fides.

The following steps will be followed for sampling of phone-survey respondents:

- 1. Exclude Firozabad which has no programme in 2020

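### The stated power is for all sampled women, but ANC practices can be compared only in women with a pregnancy that continued after enrolment, and the sampling secures no number of them

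*Protocol*

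**What the plan says.** Section 1.3 poses a maternal question next to the contraceptive one: "Does the Tiko digital platform increase consistent MNCH behaviours? Why or why not". Section 2.2 says that both surveys will be used for group mean tests "to compare SRH and ANC related practices between the two groups", meaning regular users against one-time or non-users.

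Two power statements follow. The first reads "Assuming at least 150 regular and 150 non-users included in the in-person surveys, the sample will have power to detect 25% relative change", given also as "0.25 SD change from an outcome distributed binomially with mean of 0.50". The second reads "Assuming 500 regular and 500 non-users included in the in-person surveys, the sample will have power to detect 15% relative change", given also as 0.15 SD. Both are "with power of 80% and Type I error of 0.10 with one sided test". Neither separates ANC outcomes from outcomes that every woman can supply.

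On who is sampled:

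- Section 2.1 limits participants to women aged 18-35 who took a Tiko card between 2018 and 2020. It gives the service mix only as a combined figure: "administer the in-person survey to approx. 480 beneficiaries of SRH and MCH services (total". Its aim of adequate representation concerns regular, sporadic or one-time, and non-users, not service line.
- Section 2.3 stratifies the in-person sample by user status (150 non-users, 350 users), city and agent, then says: "Obtain a list of randomly sampled Beneficiaries from Triggerise for each sampled pro agent". The phone sample is stratified by user status (500 non-users, 1,500 users) and city.
- Neither survey has a stratum, quota or screening step for MCH use or pregnancy.

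**The concern.** The platform serves women who want contraceptives or hygiene products as well as women seeking maternal care (section 1.1). A woman who enrolled for contraception and was not pregnant afterwards fills a place in the sample but has no ANC practice that the platform could have affected. Her place still counts in the 150 or 500 on which power is stated.

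The precision available for the maternal question is therefore unknown when the sample is fixed, and the only figures in the protocol are too favourable for it. A reader could take a null ANC result as evidence of little effect at the stated 0.25 or 0.15 SD when the comparison could not have detected such a difference. The number of eligible women is set by the sampling and cannot be raised at analysis.

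**Working it through.** **Inputs.** From section 2.2: 150 v 150 and 500 v 500; base proportion 0.50, so 25% relative is 0.50 v 0.625 and 15% relative is 0.50 v 0.575; or differences of 0.25 and 0.15 SD; 80% power; one-sided 0.10. The normal quantiles are 1.2816 and 0.8416, sum 2.1232. The share of women with a pregnancy that continued after enrolment is not in the documents and is an assumption below.

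The 500 v 500 sentence refers to the in-person surveys, but section 2.3 puts only 500 women in that survey in total. I read it as the phone survey, which has 500 non-users.

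**Step 1: reproduce the stated power.** For a difference of d SD, n per group = 2 × (2.1232 / d)².

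- d = 0.25: 2 × (8.493)² = 144.3, so 145. For 0.50 v 0.625 the two-proportion formula gives 142. With 150 per group, power is 81.2% (means) or 81.8% (proportions).
- d = 0.15: 2 × (14.155)² = 400.7, so 401. For 0.50 v 0.575 it is 398. With 500 per group, power is 86.2% or 86.4%.

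The stated figures are sound if every sampled woman supplies the outcome.

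**Step 2: share that must be eligible for 80% power.**

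- In person: 142/150 = 95% to 145/150 = 97%.
- 500 v 500: 398/500 and 401/500, both about 80%.

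**Step 3: detectable difference if fewer are eligible.** Detectable SD = 2.1232 × √(2/n). Assumed: 20-40% eligible in both groups, clustering ignored.

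| Source | Women per group | Eligible at 20% / 40% | Detectable SD at 20% / 40% | Stated |
|---|---|---|---|---|
| In person | 150 | 30 / 60 | 0.55 / 0.39 | 0.25 |
| Phone | 500 | 100 / 200 | 0.30 / 0.21 | 0.15 |
| Both pooled | 650 | 130 / 260 | 0.26 / 0.19 | none |

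At the same shares, power for the stated effects is about 38% / 54% in person (0.25 SD) and 41% / 59% for 500 v 500 (0.15 SD). At a more generous 50%, it is about 60% (75 per group) and 65-66% (250 per group).

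**Step 4: share the pooled surveys would need.** For 0.25 SD, 145/650 = 22% per group. For 0.15 SD, 401/650 = 62% per group.

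**The case against.** The strongest reply is that the in-person survey is not the only source. Section 2.2 assigns both surveys to this comparison and says the phone survey is there to add power. Pooled, at 20-40% eligible, they detect 0.26-0.19 SD, which is close to or better than the 0.25 SD stated for the in-person groups. The comparator is also one-time or non-users, so it may exceed 150 women. This stands. A reader might infer that the maternal question cannot be answered, and the documents do not support that. What remains is that the in-person figure does not hold for ANC at these shares, and the 0.15 SD figure is not reached even after pooling.

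It also stands that the protocol calls the analysis mainly descriptive and the comparison exploratory, and that the in-person sample was sized on a proportion (384 × 1.25). This lowers the weight of the point. It does not remove it, because section 2.2 names ANC and then states power without distinguishing it.

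Two stronger readings are tempting and should not be made:

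- *That unfinished pregnancies will be counted as ANC failures.* No passage says so. The measure of at least 4 visits appears only as an input to the cost-effectiveness models, taken from backend data. Some ANC practices, such as early registration, can be read during a pregnancy.
- *That pregnancies before enrolment will dilute the effect by a known amount.* Their share is not in the documents. The draft questionnaires (Annexures 5 and 6) are not shown and may collect pregnancy dates, which would allow such pregnancies to be excluded. In a non-randomised comparison they also carry selection differences, so the direction of the error is not assured.

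**Conclusion.** The point holds as one about the basis of the power statement and the unsecured eligible number. The arithmetic in section 2.2 is correct for outcomes that every woman can supply. It does not apply to ANC practices unless about 95% of 150, or 80% of 500, women per group had a pregnancy that continued after enrolment, and nothing in sections 2.1 to 2.3 secures that. This part needs no outside figure.

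The size of the loss does rest on an assumption. The 20-40% range is illustrative, is applied equally to both groups although users and non-users may well differ, and ignores clustering by agent and city. The pooled figures further assume that the phone questionnaire carries the same ANC items. Given the exploratory aim, this is a moderate point, best corrected before the sample lists are drawn.

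**What to change.** In section 2.2:

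1. Say that the stated power applies to outcomes defined for all sampled women.
2. Base the ANC comparison on pregnancies that continued after enrolment, with completed pregnancies only for any outcome that counts visits.
3. Restate the detectable ANC difference for the expected eligible number from both surveys. For users, the sponsor's transaction records (service and date) can inform that number. Non-users have no transactions, so a stated range is needed.

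Possible wording: *The detectable differences above apply to outcomes defined for every woman. ANC outcomes will be compared among women with a pregnancy that continued after enrolment (completed pregnancies only for visit counts); with an expected __ and __ such women in the two groups across both surveys, the detectable difference is __ SD.*

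The cost is a few sentences, a count by the sponsor, and a less favourable stated figure for ANC.

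Optionally, in section 2.3, the sponsor could draw the user lists with an SRH/MCH stratum from the transaction records, and descriptive estimates would then be weighted back to the frame. The sponsor would have to do this, because backend data reach the researchers without identifiers. The price is somewhat less SRH precision within the same total.

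A matching pregnancy screen and quota for non-users is a more debatable trade-off. It would depart further from proportional allocation, discard contacts where phone response is expected to be only 10-15%, and put a private question into the appointment call. I would not make it a condition.
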